16.3. Early Discontinuation of Study

The study may be stopped before completion as an Urgent Safety Measure on the recommendation of the TSC (see section 14.3.2 Trial Steering Committee (TSC)). Sites will be informed in writing by UCL CTC of reasons for early closure and the actions to be taken with regards the treatment and follow up of patients.

16.4. Withdrawal from Study Participation by a Site

Should a site choose to close to recruitment the PI must inform UCL CTC in writing. Follow up as per protocol must continue for any patients recruited into the study at that site and other responsibilities continue as per the site agreement.

17. STATISTICS

This is a prospective observational cohort study of patients of all ages with histopathologically confirmed OS.

17.1. Sample Size as feasibility endpoint

One of the objectives of Stage 1 was to assess the feasibility of recruiting to this cohort. Our assumption was that 15 sites would be opened during the course of the first 11 months of recruitment. Once all sites were opened (from month 12 onwards), we estimated that the average recruitment rate would be 5 patients/month.

Following the completion of Stage 1 and with the extension to the recruitment period, we expect to recruit a minimum of 300 patients to the study in total.

17.2. Statistical analysis

17.2.1. Stage 1

Descriptive analyses and tabulations have been performed to answer the Stage 1 research questions, as detailed in the table below.

Re	search question	Analysis					
Re	cruitment objective						
1.	Feasibility of recruiting patients across UK paediatric, TYA and adult centres to cohort study	Recruitment rate after opening % patients recruited according t					
Cli	nical objectives						
3.	Determine patterns of treatment of patients across UK treatment sites to inform stage 2 objectives and future studies Determine feasibility of surgical data capture to inform future studies	% patients with MDT document planned treatment % patients receiving chemother % patients undergoing surgery % patients receiving radiotheral List of possible reconstruction to relative frequencies % patients with post-operative of	apy and regimen by and indications echniques and their				
4.	 Imaging: determine primary tumour imaging and reporting pre and post chemotherapy Determine variation in imaging modalities used for staging of OS patients to inform future studies 	% patients staged with bone sca WB–MRI	n, PET/CT and/or				
Bio	ological objectives						
1.	Determine feasibility of fresh frozen tissue sample collection across sites across the UK	Collection rate per site Number and % of metastatic/re for future research % sent for WGS	lapse specimens stored				
2.	Determine quality of Formalin Fixed paraffin-embedded (FFPE) samples and feasibility of DNA/RNA extraction for validation studies	Collection rate of diagnostic/res in patients treated with surgery Audit to determine whether qua RNA/DNA sufficient for targeted nanostring analysis	and chemotherapy ality and quantity of				
3.	Evaluate whether two methodologies of circulating tumour cell (CTC) detection can isolate and quantify CTCs in patients undergoing neoadjuvant chemotherapy	Identification and quantificatior baseline (pre-treatment) and ch in response to chemotherapy Descriptive analysis of CTC num ranges (min, max, IQR, median)	anges to CTC numbers				

Re	search question	Analysis
4.	Collection of whole blood for potential methylation/ctDNA/future research	Collection rate per site
5.	Collection of whole blood for Germline DNA analysis	
6.	Evaluate collection of serum biomarkers for validation of prognostic scores	 Collection rate of serum parameters Characterisation of distribution of serum biomarkers as histograms and ranges (min, max, IQR, median)
7.	Determine feasibility of using standard pathology reporting to assess margin status for risk of local recurrence	 Collection rate of pathology reports in patients undergoing surgery Characterisation of tumour size, assessment of resection margins, % necrosis
Pa	tient Reported Outcome	
1.	Determine feasibility of data collection for validation of a sarcoma assessment measure (SAM) in patients undergoing treatment for OS	 Completion rate of SAM, TESS, EORTC-QLQ-C30 and GRC Descriptive analyses of PROs

17.2.2. Stage 2

17.2.2.1: Support and development of ICONIC infrastructure

The first aims for Stage 2 are:

- to support ongoing recruitment to the ICONIC study with additional follow up to form a cohort of a minimum of 300 patients with a median of approximately 56 months follow up
- to continue the collection of tissues and blood samples for CTC and plasma for circulating DNA (ctDNA)
- to collect peripheral blood mononuclear cells in a cohort of patients for IO research
- to establish an imaging biorepository for collaborative imaging biomarker studies.

Analysis of patient outcomes will be descriptive, using Kaplan-Meier methods for survival outcomes (e.g. overall survival, event-free survival and progression-free survival) and counts/frequencies for categorical outcomes (e.g. pathological response to chemotherapy).

Predictors of patient outcome will be assessed using standard regression techniques: Cox regression for survival outcomes, logistic regression for categorical. We will consider the following potential predictors of patient outcome:

- Blood biomarkers: serum biomics and ctDNA/CTCs
- Baseline characteristics (age, performance status, grade, primary site, tumour size, stage)
- Patterns of treatment
- Tissue biomarkers for IO research

Research questions	Planned analysis
Evaluate serum biomarkers (ALP, LDH) as prognostic markers in OS	Quantify serum biomarkers at baseline (pretreatment) and changes in response to chemotherapy.
	Characterise distribution of serum biomarkers as histograms and ranges (min, max, IQR, median)
	Assess serum biomarkers for prognostic value by using Cox regression (time-to-event outcomes) and logistic regression (categorical outcomes)
Evaluate ctDNA as predictors of response and outcome in OS	Quantify ctDNA biomarkers at baseline (pretreatment) and changes in response to chemotherapy.
	Characterise distribution of ctDNA as histograms and ranges (min, max, IQR, median)
	Assess ctDNA biomarkers for prognostic value by using Cox regression (time-to-event outcomes) and logistic regression (categorical outcomes)
Evaluate whether two methodologies of circulating tumour cell (CTC) detection can isolate and quantify CTCs in patients undergoing neoadjuvant chemotherapy	Identify and quantify CTC numbers at baseline (pretreatment) and changes to CTC numbers in response to chemotherapy Descriptive analysis of CTC numbers as histograms and ranges (min, max, IQR, median)

Power calculations for analysis of biomarkers as predictors of pathological response:

All power calculations assume a fixed 2-sided 5% significance level. As these analyses are hypothesis generating, no adjustments have been made to account for multiple testing.

Stage 1 determined the good pathological response rate to be lower than in clinical trials with 17/43 (37%) having a good response.

Based on data from England (2011-2015), 66% of patients receive surgery and 66% receive chemotherapy. At the outset of Stage 1 we had assumed that 60% of patients receive both treatments. At the end of Stage 1, we determined in our cohort that 72% of patients were planned to receive both modalities of treatment.

We will therefore assume the size of the full dataset of patients treated with both modalities will be at least 65% of 300 patients, thus 195 patients.

1. Serum biomarkers

We expect at least 90% of patients to provide serum samples for biomarker analysis, giving us a cohort size of 176. Assuming an overall pathological response rate of ~40%, and assuming biomarkers will be

categorised based on the median to give an even split (88 per group), below is a summary of the power we will have to detect varying effect sizes:

Alpha	Proportion responding without biomarker (# of responders)	Proportion responding with biomarker (# of responders)	Odds ratio	Risk ratio	Power
0.05	20% (18)	60% (53)	5.9	2.9	99.9%
0.05	25% (22)	55% (48)	3.6	2.2	98.6%
0.05	30% (26)	50% (44)	2.4	1.7	77.8%
0.05	32.5% (29)	47.5% (42)	1.9	1.4	52.9%

2. ctDNA

At the end of Stage 1, 76 patients had provided baseline samples but on treatment samples were fewer and it was not possible for all patients to have baseline samples collected prior to commencing treatment. We therefore assume that with a total sample size of 300, 150 patients will have sufficient pre-samples to correlate biomarkers with clinical characteristics. Assuming an overall pathological response rate of ~40%, and assuming biomarkers will be categorised based on the median to give an even split (75 per group), below is a summary of the power we will have to detect varying effect sizes:

Alpha	Proportion responding without biomarker (# of responders)	Proportion responding with biomarker (# of responders)	Odds ratio	Risk ratio	Power
0.05	20% (15)	60% (45)	6	3	99.9%
0.05	25% (19)	55% (41)	3.6	2.2	97.0%
0.05	30% (23)	50% (38)	2.3	1.7	70.9%
0.05	32.5% (24)	47.5% (36)	2.0	1.5	46.6%

17.2.2.2: Immune oncology

Biomarkers identified through WGS will be summarised using descriptive statistics (median, range, mean, standard deviation) and assessed as prognostic markers for infiltration (poorly infiltrated vs highly infiltrated) using logistic regression. We assume the overall proportion of patients with high infiltration will be 40% and that biomarkers will be categorised based on the median, to ensure equal numbers of those with and without the biomarker. With 2-sided 5% alpha, our power calculations show that with 150 samples we have >70% power to detect a risk ratio (RR) effect size of RR=1.7 or larger and >95% power to detect an effect size of RR=2.2 or larger. We note that the biomarkers in question here are in fact new therapeutic drug targets, where a strong effect size is required to ensure potential therapeutic efficacy, so biomarkers with more marginal effect (e.g. RR=~1.1-1.5) are not in scope for the study. Hence, we are confident that with 150 patients in our multiplex immunohistochemistry (mIHC) experiment we are well powered to validate novel targets that are significantly different between poorly and highly infiltrated patient groups.

17.2.2.3: Patient Reported Outcomes

We aim to record patient reported outcomes (PROs) over time which are correlated with clinical data for the purposes of identifying factors including prediagnostic pathways which predict lower quality of life, physical function and impaired emotional wellbeing.

PRO analyses will be largely descriptive, so no power calculation is provided. However, as with all descriptive analyses, the more data we acquire the more likely it is to describe our patient population accurately.

Re	search questions	Pla	anned analysis
1.	Describe longitudinal changes in PRO and functional wellbeing beyond a year after diagnosis	•	Quality of life questionnaires will be analysed using mixed modelling and results reported by each domain with summary statistics. Models will work with the date of assessment, rather than
2.	Determine the emotional impact of being diagnosed and living with OS		predefined timepoint, to account for varying treatment pathways.
3.	Examine the relationship between prediagnostic intervals and PROs	•	Mixed modelling will be used to assess whether prediagnostic interval is associated with quality of life post diagnosis.
4.	Identify factors predicting lower quality of life, physical function and impaired emotional wellbeing.	•	Mixed modelling will be used to assess which factors have an impact on quality of life post diagnosis.

17.3. Transition between Stage 1 and Stage 2

At the end of Stage 1, the analyses described in section 17.2.1 were performed. The analyses proposed for Stage 2 were reviewed during the transition and altered as above based on the findings.

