1. PROTOCOL SUMMARY

1.1. Summary of Study Design

Title:	Improving outcomes through Collaboration in OsteosarComa
Short Title/acronym:	ICONIC
Sponsor name & reference:	University College London Reference: 18/0248
Funder name & reference:	Bone Cancer Research Trust
Clinicaltrials.gov no:	NCT04132895
Design:	Prospective observational cohort study.
Overall aim:	To improve treatment and outcomes for patients with osteosarcoma (OS) by establishing a clinically annotated cohort of newly diagnosed patients with OS with longitudinal collection of biospecimens.
Primary objective:	To obtain high quality clinical data and biospecimen collection from OS patients to develop potential new osteosarcoma trials.
Secondary objectives:	To enrol 300-350 patients to address the following questions:
	CLINICAL OBJECTIVES
	 Describe the impact of variation in management of patients with OS across treatment sites in the UK
	 Assess whether tumour margin and response to chemotherapy predict local recurrence in OS
	BIOLOGICAL OBJECTIVES
	Assess whether OS tumour and immune models grown from OS patients can be used to identify new therapeutic targets
	Explore whether new candidate immunotherapy drug targets for OS can be discovered based on cellular and genomic analysis
	 Collect peripheral blood mononuclear cells (PBMCs) from OS patients to inform immune studies
	 Develop patient derived explants, primary cell cultures, cell lines and organoid models from fresh/frozen patient tumour tissue to investigate OS biology and validate new candidate drug targets
	 Use formalin-fixed paraffin-embedded (FFPE) samples to evaluate genetic and immune biomarkers and aid development of novel therapeutic targets and trials
	Create a legacy resource of OS immune oncology (IO) data and patient models to accelerate future collaborative research efforts

	CIRCULATING BIOMARKERS			
	 Assess whether circulating biomarkers can be used as prognostic markers and to predict burden of disease, response to therapy and outcome 			
	Determine the prevalence of Germline DNA alterations in UK OS patients			
	IMAGING OBJECTIVES			
	 Determine if standard of care imaging can be used to conduct imaging biomarker studies through establishment of an imaging repository 			
	Examine the effects of tumour heterogeneity and clonal evolution on chemotherapy response and patient outcome and determine if this can be used to stratify patients for therapy			
	PATIENT EXPERIENCE			

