	 Assess the value of the Sarcoma Assessment Measure (SAM) for longitudinal assessment of patient quality of life and identify predictors of variance in patient reported outcomes (PROs) 			
	 Describe the routes and timescales of diagnostic pathways for patients with OS, and assess whether this has any impact on patient outcome 			
Target accrual:	A minimum of 350 patients (including those already recruited in ICONIC).			
Eligibility criteria:	Inclusion criteria			
	 New histological diagnosis of osteosarcoma or in the absence of osteoid seen on biopsy, pathology and imaging supportive of a diagnosis of osteosarcoma 			
	 Written informed consent of patient and/or parent/legal guardian or written confirmation of opinion of person with duty of care where applicable 			
	Exclusion criteria			
	Diagnosis more than four months prior to registration			
Number of sites:	At least 25 sites representing OS specialist oncology and surgical sites across the UK			
Treatment summary:	Treatment will be given as per usual standard of care.			
	No treatments are specified by this protocol.			

Patient study activities:

Clinical data collection

Clinical data will be collected on a regular basis. Data to be collected include baseline characteristics, treatment details, results of key investigations (including blood tests and scans), patient status (including performance status) and outcome.

Tissue and blood collection

- Tissue for FFPE and fresh freezing according to local policy will be collected during routine procedures at diagnosis, at surgery and at relapse if clinically indicated.
 - Optional study specific biopsies will be requested at relapse in cases where a biopsy is not clinically indicated.
- Blood samples will be collected from patients receiving chemotherapy and/or surgery at the same timepoints as tissue, with an additional sample presurgery and further optional samples.

Patient Reported Outcomes (PROs)

Sarcoma Assessment Measure (SAM) questionnaire

Patients ≥13 years of age will be requested to complete a Sarcoma Assessment Measure (SAM) questionnaire along with TESS, EORTC-QLQ-C30 and Global rating of change (GRC) at registration, annually and at relapse.

Prediagnostic data collection

- Patients ≥13 years will be requested to complete a questionnaire at registration detailing symptoms and routes to diagnosis.

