3. STUDY DESIGN

This is a prospective observational cohort study in patients with osteosarcoma (OS). All newly diagnosed OS patients are eligible to take part. Consenting patients are recruited and followed up for at least two years.

The main aim of the study is to establish a platform which supports the recruitment of a consecutive cohort of newly diagnosed OS patients, whose clinical outcomes will be fully annotated and linked to their molecularly characterised biospecimens. The platform will support continuous collection, analysis and interrogation of data to generate hypothesis driven questions quickly for further evaluation. This project extends the Bone Cancer Research Trust tumour banking initiative with funding allocated to provide the infrastructure to optimise collection and storage of tissue samples in the five diagnostic and surgical bone tumour centres in England. It includes the development and validation of clinically relevant biomarkers to identify patients at high risk of relapse and patients suitable for therapeutic studies.

The study will be conducted in two stages. In **Stage 1**, we established the feasibility of patient recruitment and biospecimen collection. In **Stage 2**, correlation with response to chemotherapy and outcome will help develop prognostic biomarkers and provide an opportunity to identify patients for specific therapies. The study will continue these objectives and maintain a platform for development of additional studies and development of therapeutic studies based on the findings from our initial work.

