3.1. Study Objectives

3.1.1. Stage 1: Completed

Determined the feasibility of recruiting patients to a national study with high quality clinical data and biospecimen collection to address clinical and biological questions in OS. Its specific research objectives and associated analyses are detailed in Appendix 4 below.

3.1.2. Stage 2

To enrol >350 patients (including those enrolled in Stage 1) and to use the data and samples collected to begin to address the questions listed below.

Following completion of Stage 1 the research objectives of Stage 2 have been amended and adjusted to take into account previous findings:

- Describe variations in management of patients with OS across treatment sites in the UK, including how decisions are reached for tumours being deemed inoperable and how patients contribute to the final decision on surgical operability in terms of what surgery is acceptable.
- Describe current indications for radiotherapy (RT) as part of local therapy
- Describe the impact of variation in management of patients with OS across treatment sites in the UK on patient outcome
- Assess whether tumour margin and response to chemotherapy predict local recurrence in OS
- Use FFPE samples be used to validate WGS findings, identify patients for specific therapies and aid development of novel therapeutic trials
- Use FFPE samples to perform transcriptional and proteomic spatial profiling of OS
- Develop a legacy resource of OS IO data and patient models to accelerate future collaborative research efforts
- Establish novel *in vitro* experimental models of OS (cell lines, organoids, explants) to be used to address biological questions regarding the mechanism of response to chemotherapy and immune-directed therapies
- Create an OS IO data atlas portal
- Assess whether circulating biomarkers can be used as prognostic markers and to predict burden of disease, response to therapy and outcome
- Collect PBMCs from 20 OS patients at UCLH
- · Set up an OS imaging repository with NCITA
- Use two methodologies of circulating tumour cell (CTC) detection to isolate and quantify CTCs in a subset of 50 patients undergoing neoadjuvant chemotherapy
- Describe associations between tumour heterogeneity and clonal evolution on chemotherapy response and patient outcome and determine if this can be used to stratify patients for therapy
- Determine if Germline DNA alterations can be confirmed in OS
- Collect WGS samples for the OS population

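### Models relating patterns of treatment to outcome name no allowance for treatment site, so intervals for site-driven practices may be too narrow

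*Protocol*

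**What the plan says.** The protocol summary (section 1.1) lists as a clinical objective: "Describe the impact of variation in management of patients with OS across treatment sites in the UK". The Stage 2 list in section 3.1.2 makes the link to outcome explicit: "Describe the impact of variation in management of patients with OS across treatment sites in the UK on patient outcome". The summary gives the number of sites as "At least 25 sites representing OS specialist oncology and surgical sites across the UK", and section 17.1 states "we expect to recruit a minimum of 300 patients to the study in total".

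Section 17.2.2.1 first calls the analysis of patient outcomes descriptive (Kaplan-Meier curves, counts and frequencies). It then adds regression: "Predictors of patient outcome will be assessed using standard regression techniques: Cox regression for survival outcomes, logistic regression for categorical". The candidate predictors are blood biomarkers, baseline characteristics (age, performance status, grade, primary site, tumour size, stage), "Patterns of treatment" and tissue biomarkers. Primary site here means the tumour's location, not the hospital. For these models the protocol names no treatment-site term, frailty, stratification or robust variance. Models for correlated data appear only in section 17.2.2.3, as mixed models for patient-reported outcomes.

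**The concern.** The objective relates outcome to practices that differ between hospitals. Patients at one hospital may share case mix, surgical and chemotherapy practice, reading of margins and necrosis, and follow-up habits. Ordinary Cox and logistic models count each patient as a separate piece of information. For an exposure that is wholly or partly a feature of the site, this overstates the information and understates the standard error.

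At stake is whether a difference between sites is reported as an effect of a practice when it is only ordinary variation between sites. This has consequences: section 2.3 intends to address variation in the delivery of standard therapy and to stimulate pilot interventions in areas identified from the clinical data.

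**Working it through.** **The plan's own figures.** The protocol gives no sample size, power or error rate for the site question. Its only power figures are for median-split biomarkers against pathological response. They reproduce with the usual two-proportion formula (two-sided 5%, pooled null variance, no continuity correction). Example with 88 per group, 30% v 50%: null SE = √(2 × 0.4 × 0.6/88) = 0.0739; alternative SE = √((0.21 + 0.25)/88) = 0.0723; (0.20 − 1.96 × 0.0739)/0.0723 = 0.76; power 77.8%, as stated. In full, the serum powers come to 99.99, 98.6, 77.8 and 52.9%, and the ctDNA powers to 99.96, 97.0, 70.9 and 46.6%. The stated values agree closely. These tables are not affected by what follows.

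**Inputs for the site question**
- Patients: 300 (section 17.1). The summary gives 350 as the minimum, used below as a sensitivity value.
- Sites: 25, the minimum in section 1.1. Average per site: m = 300/25 = 12.
- Patients treated with both modalities: 195 (section 17.2.2.1), so m = 195/25 = 7.8.
- ICC: **not in the documents**; assumed 0.01 to 0.10.
- Reference level: 5% two-sided. This is a yardstick only, since the protocol sets no level for this objective.

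**Practice fixed by site, site ignored**

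Design effect DE = 1 + (m − 1) × ICC. Actual error = 2 × (1 − Φ(1.96/√DE)). Ratio of the naive to the correct interval width = 1/√DE.

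| ICC | DE (m = 12) | Actual error | Naive 95% interval too narrow by |
|---|---|---|---|
| 0.01 | 1 + 11 × 0.01 = 1.11 | 6.3% | 1 − 1/√1.11 = 5% |
| 0.05 | 1 + 11 × 0.05 = 1.55 | 11.5% | 1 − 1/√1.55 = 20% |
| 0.10 | 1 + 11 × 0.10 = 2.10 | 17.6% | 1 − 1/√2.10 = 31% |

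Sensitivity at ICC 0.01 / 0.05 / 0.10: with 350 patients (m = 14) the error is 6.5 / 12.7 / 19.6%; with the 195 patients (m = 7.8) it is 5.8 / 9.0 / 13.0%. More than 25 sites would make clusters smaller and the inflation less.

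For the error to reach 10%, DE must be (1.96/1.645)² = 1.42, so ICC = 0.42/11 = 0.038 at m = 12.

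**Simulation check.** Binary outcome, no true effect, random site intercepts, 300 patients, 25 sites of equal expected size, naive log-odds-ratio test, 2000 replicates per setting. The ICC is on the latent logistic scale, so agreement with the formula is approximate. Monte Carlo error near 5% is √(0.05 × 0.95/2000), about 0.5 points.

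| Exposure | ICC 0 | 0.02 | 0.05 | 0.10 |
|---|---|---|---|---|
| Fixed by site | 5.6% | 7.6% | 11.8% | 15.0% |
| Varies within site (site propensity uniform on 0 to 1) | 5.2% | 6.5% | 6.6% | 8.6% |
| Unrelated to site | 5.2% | 5.2% | 5.1% | 6.2% |

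With unequal sites (coefficient of variation 0.7) and an exposure fixed by site, the rates at ICC 0.02 / 0.05 / 0.10 are 8.7 / 12.8 / 19.8%. With an exposure that varies within sites they are 5.2 / 6.1 / 9.8%.

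This check is for a binary outcome. A Cox model is affected in the same direction, but the size depends on frailty variance and event numbers that the protocol does not give.

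**The case against.** The best defence is that the protocol names model families, not model formulas. A stratified or shared-frailty Cox model is still Cox regression, robust variance is an option in both models, and such detail is commonly settled in a statistical analysis plan, which is not at hand. This stands to a degree: the text never says that patients from one site will be treated as independent, and a reader who concludes so is inferring it. But the section does fix the model class and list the predictors, and it specifies correlated-data models elsewhere. A plan that followed it literally would have no site term.

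Second, the objective says describe, and no test is attached to it. A reader might infer that a stated 5% level is being missed. It is not: "All power calculations assume a fixed 2-sided 5% significance level" belongs to the biomarker power calculations. The concern is therefore about interval width, with the error rate as a way to show its size. Calling the work descriptive or hypothesis generating does not make a too-narrow interval correct.

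Third, management is not simply a property of the site. Treatment is recorded per patient; section 2 says it varies with age, primary site, stage and performance status; section 8 refers all sites to the same national guidelines. This stands, and it is why the smaller figures for treatment varying within sites matter as much as the larger ones.

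Fourth, a reader might take the "five diagnostic and surgical bone tumour centres in England" as the real clusters and compute a far larger inflation. Section 3 mentions those centres only in connection with tissue collection and storage. It does not say that they set management.

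**Conclusion.** The point holds in a conditional form. For a question about practices that differ between sites, the protocol prescribes standard Cox and logistic regression and names no allowance for site. If site is ignored and outcomes are correlated within it, intervals for site-driven practices are too narrow. Over an assumed ICC of 0.01 to 0.10 with 300 patients in 25 equal sites, the actual error at a nominal 5% is about 6% to 18% when a practice is fixed by site, and about 6.5% to 9% when treatment varies within sites (ICC 0.02 to 0.10). It is near nominal for patient-level predictors.

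A reader might infer that false positives double as a rule. The documents do not support that: they give no ICC, and doubling needs a practice fixed or nearly fixed by site and an ICC of about 0.04 with 12 patients per site. This is a worthwhile, inexpensive improvement to one set of models. It does not undermine the study.

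**What to change.** Add to section 17.2.2.1: *Models relating patterns of treatment or site management to outcome will account for treatment site, using a shared-frailty Cox model and a random-intercept logistic model, or site-clustered standard errors with a small-sample correction. They will be adjusted for the baseline characteristics listed above, and the between-site variation will be reported.* The text should also say which unit counts as the treatment site.

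Biomarker models and their power tables stay as they are. No new data are needed: the Sarcoma MDT site is recorded at registration (section 7) and the hospital of surgery on the surgery eCRF (section 9.3.1). The cost is a wording change, minor programming, and somewhat wider intervals for management variables.
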